#### **4.2.3.2 Stratification**

Sensitivity analyses of the primary endpoints will be performed to assess the impact of stratification. These analyses will follow the same analysis methods as the primary endpoints with the exception that IRF-assessed PFS will be compared using an unstratified log-rank test and the HR will be estimated from an unstratified Cox proportional hazards model.

#### **4.2.4 Supplementary Analyses**

The following supplementary analyses will be performed on IRF-assessed PFS in the PPAS and FAS to provide additional insights into the understanding of the treatment effect.

##### **4.2.4.1 Subgroup Analyses for Primary Endpoints**

The generalizability of IRF-assessed PFS results when comparing the tiragolumab plus atezolizumab arm to the durvalumab arm will be examined by estimating the treatment effect in [REDACTED]

[REDACTED]

### 4.3 SECONDARY ENDPOINTS ANALYSES

The secondary efficacy endpoints will be analyzed in the PPAS and the FAS, and the statistical testing of the hypotheses depends on the results of the primary endpoint analyses. The estimands for selected secondary endpoints are defined in [Table 2](#).

#### 4.3.1 Key Secondary Endpoints

##### 4.3.1.1 Overall Survival

OS is defined as the time from randomization to death from any cause. Data for patients who are not reported as having died at the time of the analysis will be censored at the date when they were last known to be alive. Patients who do not have post-baseline information will be censored at the date of randomization.

OS will be analyzed through use of the same methods described for the IRF-assessed PFS analysis.

If IRF-assessed PFS is statistically significant in the PPAS but not in the FAS, OS in the PPAS will be assessed descriptively.

The details of analysis timing for OS are described in [Section 4.7](#).

##### 4.3.1.2 Investigator-Assessed Progression-Free Survival

Investigator-assessed PFS is defined as the time between the date of randomization and the date of first documented disease progression, as assessed by the investigator according to RECIST v1.1, or death, whichever occurs first. Patients who have not experienced disease progression or death at the time of analysis will be censored at the time of the last tumor assessment. Patients with no post-baseline tumor assessment will be censored at the date of randomization.

INV-assessed PFS will be analyzed through use of the same methods described for the IRF-assessed PFS analysis.

##### 4.3.1.3 Objective Response Rate

###### 4.3.1.3.1 IRF-Assessed Objective Response Rate

A confirmed objective response is defined as either a complete response (CR) or partial response (PR) on two consecutive occasions  $\geq 4$  weeks apart, as determined by the IRF according to RECIST v1.1. Patients who do not meet these criteria, including patients without any post-baseline tumor assessment, will be considered non-responders.

Confirmed objective response rate (ORR) is defined as the proportion of patients who achieve a confirmed objective response. Confirmed ORR will be analyzed in the randomized patients with measurable disease at baseline.

An estimate of confirmed ORR and its 95% CI will be calculated using the Wilson score method for each treatment arm. CIs for the difference in confirmed ORRs between the two treatment arms will be determined using the Newcombe method. The confirmed ORR will be compared between the two treatment arms using the stratified Mantel-Haenszel test. The stratification factors of this analysis will be the same as those described in Section [4.2.2](#)

#### **4.3.1.3.2 Investigator-Assessed Objective Response**

Confirmed ORR as determined by the INV according to RECIST v1.1 will also be analyzed. The analysis methods will be the same as those described for IRF-assessed ORR.

#### **4.3.1.4 Duration of Response**

##### **4.3.1.4.1 IRF-Assessed Duration of Response**

Duration of response (DOR) will be assessed in patients who achieved a confirmed objective response, as determined by the IRF according to RECIST v1.1. Duration of response is defined as the time interval from the date of the first occurrence of a confirmed objective response until the first date of progressive disease as determined by the IRF according to RECIST v1.1 or death from any cause, whichever occurs first. Patients who have not progressed and who have not died at the time of analysis will be censored at the time of last tumor assessment date. Duration of response will be based on a non-randomized subset of patients (specifically, patients who achieve a confirmed objective response); therefore, formal hypothesis testing will not be performed for this endpoint. Comparisons between treatment arms will be made for descriptive purposes.

Median DOR and corresponding 95% CIs will be estimated using Kaplan-Meier methodology for each treatment arm.

##### **4.3.1.4.2 Investigator-Assessed Duration of Response**

DOR for patients with confirmed objective response, as determined by the INV according to RECIST v1.1, will also be analyzed. The analysis methods will be the same as those described for IRF-assessed DOR.

For TTCD, data for patients will be censored at the last time when they completed an assessment if they have not experienced a confirmed clinically meaningful deterioration event at the clinical cutoff date, or a clinically meaningful deterioration immediately followed by death due to progressive disease within 6 weeks. If no baseline or post-baseline assessment is performed, patients will be censored at the randomization date. TTCD using the EORTC scale will be analyzed using the same methods as for PFS.

## **4.3.2            Sensitivity Analyses for Key Secondary Endpoints**

### **4.3.2.1        Stratification**

Sensitivity analyses of INV-assessed PFS and OS will be performed to assess the impact of stratification. The analyses will follow the same analysis methods as the primary endpoints with the exception that INV-assessed PFS and OS will be compared using an unstratified log-rank test and the HR will be estimated from the unstratified Cox proportional hazards model.

### **4.3.3 Supplementary Analyses for Key Secondary Endpoints**

#### **4.3.3.1 Subgroup Analysis for Secondary Endpoints**

The generalizability of OS results when comparing the tiragolumab plus atezolizumab arm to the durvalumab arm will be examined by estimating the treatment effect in

[REDACTED]

[REDACTED]

#### **4.3.3.2 Non-Protocol Anti-Cancer Therapy for Overall Survival**

The impact of subsequent non-protocol anti-cancer therapy (NPT) on OS will be assessed depending on the number of patients who received NPT. If > 10% of patients received NPT in either treatment arm, the discount method may be performed to compare treatment arms. The discount method uses a 'discounted' survival time after switching for patients who switch treatments based on a user-specified assumption for the effect on OS. OS may be discounted according to a range of possible effects on OS of the subsequent NPT after treatment switching occurred (e.g. 10%, 20%, 30%, etc.).

### **4.3.4 Supportive Secondary Endpoints**

#### **4.3.4.1 Progression-Free Survival Rate at Landmark Timepoints**

The IRF-assessed PFS rate and investigator-assessed PFS rate at 12, 18 and 24 months after randomization will be estimated using Kaplan-Meier methodology for each treatment arm and the 95% CIs calculated using the standard error derived from Greenwood's formula. The 95% CI for the difference in PFS rates between the two treatment arms will be estimated using the normal approximation method, with standard errors computed using Greenwood's method.

#### **4.3.4.2 Overall Survival Rate at Landmark Timepoints**

The OS rate at 12, 24, 36, 48 months will be estimated using Kaplan-Meier methodology for each treatment arm and the 95% CIs calculated using the standard error derived from Greenwood's formula. The 95% CI for the difference in OS rates between the two treatment arms will be estimated using the normal approximation method, with standard errors computed using Greenwood's method.

#### **4.3.4.3 Time to Death or Distant Metastasis**

Time to death or distant metastasis (TTDM) is defined as the time between the date of randomization and the date of first documented distant metastasis as assessed by investigator according to RECIST v1.1, or death, whichever occurs first. Specifically, distant metastasis is defined as any new lesion that is outside of the radiation field.

Patients who have not experienced distant metastasis nor died at the time of analysis

Tiragolumab and Atezolizumab—F. Hoffmann-La Roche Ltd

Statistical Analysis Plan GO41854

will be censored at the time of the last tumor assessment. Patients with no post-baseline tumor assessment will be censored at the date of randomization. Comparisons between treatment arms will be made for descriptive purposes.

Kaplan-Meier methodology will be used to construct survival curves for each treatment arm and to estimate median TTDM for each treatment arm. The Brookmeyer-Crowley methodology will be used to construct the 95% CI for the median TTDM for each treatment arm (Brookmeyer and Crowley 1982). Additionally, the TTDM rate at selected time points at 12, 24, 36, 48 months will be provided.

#### **4.4 EXPLORATORY ENDPOINTS ANALYSIS**

[REDACTED]

[REDACTED]

[REDACTED]

#### **4.5 SAFETY ANALYSES**

Unless specified otherwise, safety analyses described below will be conducted for the SAS (see Section 3), with patients grouped according to the actual treatment received. Specifically, a patient will be included in the tiragolumab plus atezolizumab arm in the safety analyses if the patient receives any amount of tiragolumab or atezolizumab, regardless of the initial treatment assignment at randomization.

##### **4.5.1 Extent of Exposure**

Study drug exposure, including treatment duration, dosage, and dose intensity, will be summarized by treatment arm and for each study drug with descriptive statistics.

##### **4.5.2 Adverse Events**

Verbatim description of AEs will be mapped to the Medical Dictionary for Regulatory Activities (MedDRA) thesaurus terms. Severity for all treatment-emergent AEs will be graded by the investigator according to National Cancer Institute Common Terminology Criteria for Adverse Events (NCI CTCAE) v5.0, and severity for cytokine release

syndrome (CRS) will also be graded by the investigator according to the American Society for Transplantation and Cellular Therapy (ASTCT) consensus grading scale.

All AEs will be summarized by treatment arm and NCI CTCAE grade. Cytokine-release syndrome will also be summarized by treatment arm and ASTCT consensus grade. In addition, common AEs, treatment-related AEs, serious adverse events (SAEs), AEs leading to study treatment discontinuation or interruption, Grade 3-4 AEs, and fatal AEs (Grade 5) will be summarized accordingly. For the purpose of analyses, adverse event of special interest (AESI) are identified by a set of comprehensive definitions using standardized MedDRA queries (SMQs), High-Level Terms (HLT), Preferred Terms (PTs) and Sponsor-defined custom events (CEs) from the AE clinical database by medical concept. Multiple occurrences of the same event will be counted once at the maximum severity.

For the safety analyses, “treatment-emergent” is defined as AEs occurring on or after the first dose of study drug treatment or as a pre-existing condition that worsened on or after the first dose of the study treatment up to the data cutoff date.

Listings of AEs will include all treatment emergent AEs up to the data cutoff date.

All deaths and causes of death will be summarized by treatment arm.

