As of the primary clinical cutoff date, 30 June 2019, a total of 135 patients with a PD-L1 TPS $\geq 1\%$ were included in the intent-to-treat (ITT) population and were randomly assigned to receive tiragolumab plus atezolizumab (n=67) or placebo plus atezolizumab (n=68). Of the enrolled patients, 43.0% of patients had a TPS $\geq 50\%$ relative to 57.0% of patients with a TPS 1%–49%, 59.3% had non-squamous histology compared with 40.7% of patients who had squamous histology, and 10.4% of patients were never smokers versus 89.6% who had smoked. The three stratification factors were well balanced between treatment groups. Demographics were also generally well balanced between treatment arms, with a median age of 68 years in both the tiragolumab plus atezolizumab and placebo plus atezolizumab arms. There were more females (41.8% vs. 29.4%) and more White patients (62.7% vs. 58.8%) in the tiragolumab plus atezolizumab arm compared with the placebo plus atezolizumab arm.

At the primary analysis in the ITT population, 48% of patients in the tiragolumab plus atezolizumab arm compared with 28% of patients in the placebo plus atezolizumab arm were still receiving study treatment. In the TPS $\geq 50\%$ population, 65.5% of patients in the tiragolumab plus atezolizumab arm relative to 24.1% of patients in the placebo plus atezolizumab arm were still receiving study treatment.

In all randomized patients with TPS $\geq 1\%$, confirmed ORR was higher in the tiragolumab plus atezolizumab arm (31.3%) than in the placebo plus atezolizumab arm (16.2%); investigator-assessed PFS was improved in the tiragolumab plus atezolizumab arm compared with that in the placebo plus atezolizumab arm (stratified HR: 0.57; 95% CI: 0.37 to 0.90; median PFS: 5.4 vs. 3.6 months, respectively).

The improvement in ORR and PFS observed with the combination of tiragolumab and atezolizumab compared with placebo plus atezolizumab appears to be driven by the subgroup of patients with high PD-L1 expression (TPS $\geq 50\%$). In the subgroup of patients with TPS $\geq 50\%$, the confirmed ORR was higher in the tiragolumab plus atezolizumab arm (n=29; 55.2% [95% CI: 35.4% to 75.0%]) than in the placebo plus atezolizumab arm (n=29; 17.2% [95% CI: 1.8% to 32.7%]). Investigator-assessed PFS was also improved in the tiragolumab plus atezolizumab arm relative to the placebo plus atezolizumab arm (unstratified HR: 0.33; 95% CI: 0.15 to 0.72; median PFS: not reached vs. 3.9 months, respectively).

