Patients whose tumors have a known *EGFR* mutation or *ALK* rearrangement will be excluded from enrollment in this study. Patients with tumors of non-squamous histology with unknown *EGFR* or *ALK* mutational status will be required to be tested prior to enrollment (see the specific inclusion criteria in Section 4.1.1). Patients with tumors of squamous histology who have an unknown *EGFR* or *ALK* mutational status will not be required to be tested (see the specific inclusion criteria in Section 4.1.1).

Patients must have histologically or cytologically documented NSCLC who present with locally advanced, unresectable (Stage III) disease (according to 8th revised edition of the AJCC [Amin et al. 2017]/UICC NSCLC staging system).

[REDACTED]

[figure not shown]
Eligible patients will be randomized in a 1:1 ratio to receive either atezolizumab plus tiragolumab or durvalumab.

Eligible patients will be stratified by ECOG Performance Status (0 vs. 1), PD-L1 expression, [REDACTED] tumor histology (non-squamous vs. squamous), and staging (Stage IIIA vs. Stage IIIB or IIIC).

In the experimental arm, atezolizumab will be administered to patients by IV infusion at a fixed dose of 1680 mg, followed by tiragolumab at a fixed dose of 840 mg administered by IV infusion on Day 1 of each 28-day cycle for a maximum of 13 cycles (see Figure 2).

In the comparator arm, patients will receive durvalumab 10 mg/kg Q2W administered by IV infusion on Days 1 and 15 of each 28-day cycle for a maximum of 13 cycles (not to exceed 26 doses) or fixed dose durvalumab at 1500 mg every 4 weeks (Q4W) (for patients whose weight \geq 30 kg), administered by IV infusion on Day 1 of each 28-day cycle for a maximum of 13 cycles (see Figure 2). [REDACTED]

Figure 2 Dosing Schedule for Experimental and Comparator Arms

D = day; Q2W = every 2 weeks; Q4W = every 4 weeks.

* On Day 15 of each 28-day cycle, patients in the comparator arm on Q2W durvalumab dosing will receive durvalumab 10 mg/kg IV.

** For patients whose weight ≥ 30 kg.

Treatment may be continued for 13 cycles, in the absence of metastatic disease, as long as patients are experiencing clinical benefit, as assessed by the investigator, in the absence of unacceptable toxicity or symptomatic deterioration attributed to disease progression after an integrated assessment of radiographic data, biopsy results (if available), and clinical status.

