**Table 2 Other Secondary and Exploratory Objectives and Endpoints**

Other Secondary Objectives	Corresponding Endpoints
To evaluate the efficacy of tiragolumab plus atezolizumab compared with durvalumab in the PPAS and the FAS	
 
• PFS rate at 12, 18, and 24 months, defined as the proportion of patients who have not experienced disease progression or death from any cause at 12, 18, and 24 months, as determined by an IRF and investigator according to RECIST v1.1
 
• OS rate at 12, 24, 36, and 48 months, defined as the proportion of patients who have not experienced death from any cause at 12, 24, 36, and 48 months
 
• TTDM, defined as the time from the date of randomization until the date of first documented distant metastasis, as assessed by investigator according to RECIST v1.1, or death, whichever occurs first. Distant metastasis is defined as any new lesion that is outside of the radiation field.
 

To evaluate the safety and tolerability of tiragolumab plus atezolizumab compared with durvalumab	
 
• Incidence and severity of adverse events with severity graded according to the NCI CTCAE v5.0
 
 
Severity for CRS will also be determined according to the ASTCT CRS Consensus Grading Scale.

Exploratory Objectives	Corresponding Endpoints
[REDACTED]	
 
• [REDACTED]
 

[REDACTED]	
 
• [REDACTED]
 

[REDACTED]	
 
• [REDACTED]
 

Exploratory Objectives	• Corresponding Endpoints
[REDACTED]	
 
• [REDACTED]
 
• [REDACTED]
 

[REDACTED]	
 
• [REDACTED]
 

[REDACTED] ASTCT = American Society for Transplantation and Cellular Therapy;  
CRS = cytokine release syndrome; [REDACTED]

[figure not shown]
13; FAS = full analysis set; [REDACTED]

IRF = Independent Review Facility; NCI CTCAE = National Cancer Institute Common Terminology Criteria for Adverse Events; OS = overall survival; PFS = progression-free survival; PK = pharmacokinetic; PPAS = programmed death-ligand 1-positive analysis set; [REDACTED]  
[REDACTED] RECIST = Response Evaluation Criteria in Solid Tumors; TTDM = time to distant metastasis; v = version

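### AE incidence is summarised by arm with no allowance for time at risk, so longer PFS on the combination would show as a modest AE excess even at equal AE rates

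*SAP*

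**What the plan says.** The safety endpoint in SAP Table 2 is "Incidence and severity of adverse events with severity graded according to the NCI CTCAE v5.0", under an objective that compares the combination with durvalumab. SAP Section 4.5.2 delivers it as by-arm summaries: "All AEs will be summarized by treatment arm and NCI CTCAE grade". The same section treats SAEs, Grade 3-4 events, fatal events and events leading to discontinuation or interruption likewise. Its counting rule is "Multiple occurrences of the same event will be counted once at the maximum severity". Together with the word incidence, this points to proportions of patients, although the SAP does not use that phrase.

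Exposure is handled separately in SAP Section 4.5.1: "Study drug exposure, including treatment duration, dosage, and dose intensity, will be summarized by treatment arm and for each study drug with descriptive statistics". It is not used as a denominator for AEs. No safety hypothesis test is planned.

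Four provisions bear on time at risk:

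- **Cap.** Both arms stop at 13 cycles. For the experimental arm, Protocol Section 3.1.1 has the drugs "administered by IV infusion on Day 1 of each 28-day cycle for a maximum of 13 cycles".
- **Progression.** Protocol Section 3.3 ends treatment at RECIST progression, unacceptable toxicity or 13 cycles, whichever is first. Protocol Section 3.1.2 lets patients who meet its criteria continue past RECIST progression, up to the same cap. SAP Section 1.2 ties continuation to clinical benefit and absence of metastatic disease.
- **Collection.** Under Protocol Section 5.4.2.2, SAEs are reported until 90 days after the last dose or the start of new systemic anti-cancer therapy, whichever is first. AESIs are reported for 90 days whether or not new therapy starts. The window for all AEs is redacted.
- **Treatment-emergent definition.** SAP Section 4.5.2 runs it from first dose to data cutoff, with no limit tied to the last dose. For a pre-existing condition the wording is "worsened on or after the first dose of the study treatment up to the data cutoff date".

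**The concern.** Progression can end treatment, and it can also close SAE reporting when new systemic therapy starts. The arm with longer PFS therefore tends to be observed for longer, and longer PFS on the combination is the trial's hypothesis. A count-once proportion rises with length of observation, so equal underlying AE rates would be displayed as more AEs on the combination. If the combination were instead stopped earlier for toxicity, the same tables would lean the other way. The separate exposure table shows that a gap exists, but a first-event proportion cannot be corrected from mean durations.

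The reporting window adds to the difficulty. The treatment-emergent period runs to data cutoff while routine collection closes earlier, so a reader of the tables cannot tell how long each patient was at risk.

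**Working it through.** The plan states no figure to reproduce, and its design hazard ratio and control median are redacted. The check therefore asks how large the apparent excess would be if AE rates were truly identical.

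**Inputs**

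- Treatment cap T: 13 × 28 = 364 days = 11.96 months (Protocol Section 3.1.1).
- Control median PFS: 16.8 months, from the durvalumab trial in Protocol Section 1.2.2 (proxy; 10 to 24 months also tried).
- PFS hazard ratio: 0.57, 0.65 and 0.75 (assumed; 0.57 is the Phase II value in Protocol Section 1.6.2.3; 0.50 to 0.85 in the wider grid).
- Control Grade 3-4 incidence: 30.5% (Protocol Section 1.2.2; proxy; 10% to 90% in the wider grid).
- Exponential PFS (SAP Section 2.2.2) and about 400 patients per arm (800 randomised 1:1).
- Post-dose window w: 30 days (0.986 months) or 90 days (2.957 months), assumed.
- Every patient stops at progression or the cap, which gives the largest gap.

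**Step 1: time on treatment.** With λ = ln2/16.8 = 0.04126 per month in the control arm and HR × λ in the other, mean time = (1 − exp(−λT))/λ.

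- Control: 9.44 months.
- HR 0.75: 10.00 months (+5.9%).
- HR 0.65: 10.23 months (+8.4%).
- HR 0.57: 10.42 months (+10.4%).

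Without the cap the ratios would be 1/HR, that is 1.33, 1.54 and 1.75. The shared cap removes most of the gap.

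**Step 2: incidence at an identical AE hazard μ.**

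P(AE) = 1 − exp(−μw) × [λ/(λ+μ) × (1 − exp(−(λ+μ)T)) + exp(−(λ+μ)T)]

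Setting the control value to 30.5% with the 30-day window gives μ = 0.0358 per month. Using the same μ with HR × λ:

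| HR | Control | Experimental | Excess, points |
|---|---|---|---|
| 0.75 | 30.5% | 32.0% | 1.5 |
| 0.65 | 30.5% | 32.6% | 2.1 |
| 0.57 | 30.5% | 33.1% | 2.6 |

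**Step 3: sensitivity**

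- 90-day window: the excess at HR 0.75 to 0.57 falls to 1.2 to 2.2 points.
- A further discontinuation hazard of 0.03 per month in both arms (30-day window): 1.3 to 2.3 points.
- All AE risk in the first 3 months, none counted after the last dose: 0.4 to 0.8 points.
- Wider grid (medians 10 to 24 months, HR 0.50 to 0.85, control incidence 10% to 90%): 0.2 to 7.6 points, the maximum at median 10 months, HR 0.50 and incidence 60%.

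**Scale.** The 95% half-width for a difference at 30.5% is 1.96 × √(2 × 0.305 × 0.695/400) = 6.4 points. The Grade 3-4 difference between durvalumab and placebo in the cited trial was 30.5 − 26.1 = 4.4 points.

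**Step 4: which remedy removes the effect**

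- First-event rates per patient-year give a ratio of 1.00 when the hazards are constant and equal. When equal risk is confined to the first 3 months, they give about 0.93 to 0.96 (HR 0.57 to 0.75), because the longer-exposed arm adds event-free time.
- Cumulative incidence at 12 months with discontinuation as a competing event, and no post-dose window, is μ/(μ+λ) × (1 − exp(−12(μ+λ))). This is the crude proportion again: at μ = 0.05 and HR 0.70 it gives 36.5% versus 38.8%.
- Cumulative incidence with censoring at the window's end does not depend on how long each arm stays on treatment, provided the censoring is non-informative.

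**The case against.** The strongest reply is that nothing inferential is distorted. The stated endpoint is incidence and severity, the SAP reports exactly that, the summaries are descriptive, and treatment duration and dose intensity appear by arm. That stands, and it limits the point to an improvement in reporting. Calling the safety comparison confounded or invalid would go further than the documents allow.

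A reader might infer that time at risk simply ends at progression. The documents do not support that: both arms stop at 13 cycles, Protocol Section 3.1.2 allows treatment past RECIST progression, SAEs can be collected for up to 90 days after the last dose, and AESIs are collected for 90 days regardless of new therapy. With the all-AE window redacted, its link to new therapy cannot be asserted. Assuming that every patient stops at progression puts the figures on the high side.

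A reader might also take the Phase II result in Protocol Section 1.6.2.3, "48% of patients in the tiragolumab plus atezolizumab arm compared with 28% of patients in the placebo plus atezolizumab arm were still receiving study treatment", as the exposure gap to expect here. It is a snapshot at a data cutoff in previously untreated locally advanced or metastatic disease, with median PFS of 5.4 versus 3.6 months and no 13-cycle cap described. It illustrates the mechanism, not the size in this trial.

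The constant AE hazard is likewise an assumption without support in the plan. What remains is the direction: under the model the excess keeps the same sign across the grid, and a larger sample would not remove it.

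**Conclusion.** The point holds in a limited form. The plan makes no allowance for time at risk in its AE comparison, and time at risk partly follows the primary endpoint. If the combination prolongs PFS, equal AE rates would show as an excess of about 1.5 to 2.6 points at a 30.5% Grade 3-4 incidence, well inside the 6.4-point half-width, and under 1 point if risk is early. This rests on a proxy control median, hazard ratio and AE incidence, an assumed 30-day window, a constant AE hazard and universal stopping at progression. It is a minor reporting gap, worth closing because closing it is cheap. It does not show that the planned tables are wrong as descriptions.

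**What to change.** Keep the crude percentages in SAP Section 4.5.2 as description. For Grade 3-4 AEs, SAEs and AESIs at least, add:

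- first-event rates per 100 patient-years, counting time from first dose to first event or the end of that event type's reporting window; and
- cumulative incidence of first event at 6 and 12 months, censoring at the end of that window, with death as the competing event.

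State the window for each event type. Do not treat discontinuation as a competing event: collection continues after it, and Step 4 shows that doing so reproduces the crude proportion. Present both summaries together, since patient-year rates favour the longer-exposed arm when events come early.

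The cost is SAP wording and a few extra tables from dates already collected. The remaining weakness is that censoring at the window's end assumes it is non-informative, which is doubtful where the window closes because of progression or toxicity; the SAP should say so.

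Separately, Protocol Sections 3.1.2 and 3.3 differ on whether treatment may continue after RECIST progression. They must be reconciled, because they imply different time on treatment.
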